Sweet consumption and subsequent sweet food preferences and intakes:

Protocol

Study ID number: NCT05672017

Document date: 31.05.25.

Design

This study utilised a parallel-groups, randomised controlled trial design with three arms. Participants were randomised to either increase, decrease or make no change to their daily intake of sweet-tasting foods and beverages for 6 consecutive days. All outcomes were assessed at two time points, on day 0 (baseline) and day 7 (end), alongside measures of adherence to the assigned diet.

Participants

A priori power calculations were based on changes in pleasantness ratings of approximately 6–9 mm (SD = approx. 13–17 mm), as reported in response to sweet taste exposure over 6 d in two previous studies(12,17) . For a two-sided α of 0·05 and power of 0·8, these calculations estimated the need for forty participants per intervention group. Eligibility criteria for the study were being over the age of 18 years, non-vegan and non-smoker, regularly consuming breakfast, having no food allergies, not pregnant or breastfeeding, not dieting or trying to lose weight and being willing and able to undertake all study requirements.

Participants were recruited using personal contacts, posters and online advertisements and through internal research volunteering platforms. To conceal our specific interest in sweet foods, the trial was described as a study of 'Eating Behaviours' with candidates advised that they would be required to modify specific aspects of their diet as instructed, although details of the modification were not given at this stage. In advance of participation, all interested candidates received study information and consent documents, and all participants provided written informed consent. The trial was designed and conducted according to the guidelines laid down in the Declaration of Helsinki (1983), the Ethical Guidelines of the British Psychological Society and the Research Ethics Codes of Practice of Bournemouth University, UK, and the University of Bristol, UK. All procedures involving human participants were approved by the Research Ethics Committees of Bournemouth University (ID: 47051/48807/45568) and the University of Bristol (ID: 06121760961) prior to commencement. Risk assessments were carried out before data collection, with regular reviews undertaken throughout the trial and all risks addressed accordingly.

Intervention/control

Participants were allocated to one of three trial arms: 'increase sweet food consumption', 'decrease sweet food consumption' and 'no diet change'(control). In the 'increase sweet food consumption' arm, participants were instructed to increase their consumption of sweet foods and beverages with the instruction 'Please increase your consumption of all sweet foods and drinks'. Participants were given examples of foods and beverages, taken from the SensoryDiet database(18) , which would be suitable to consume at different meals, including fruit, some sweet vegetables (e.g. tomatoes, sweetcorn, carrots), low-calorie-sweetened foods and beverages and some sugar-sweetened foods and beverages. In the 'decrease sweet food consumption' arm, participants were instructed to decrease their consumption of sweet foods and beverages with the instruction 'Please reduce your consumption of all sweet foods and drinks' and were given examples of non-sweet foods and beverages that would be suitable to consume at different meals, as above. Importantly, the foods highlighted to participants in these two groups were given only as examples. In addition, each participant was encouraged to judge for themselves which foods would be appropriate for them to consume to adjust the taste of their diet as requested. The purpose of this procedure was to ensure that the intervention was experienced by each participant as intended (i.e. as sweet or not sweet). This avoided imposing the researchers' assumptions about the foods

that are experienced as tasting sweet v. not sweet by each individual. For those in the control arm, no dietary change was required. Participants were simply asked to 'Continue consuming all foods and drinks that you were consuming last week'. Intervention instruction guides were provided to participants in written form for them to take away and refer to as they wished. In addition, on receipt of their instructions, participants were reminded that the aim of the study (as disclosed during consent procedures) was to investigate the effects of a dietary change and were asked to make this change as substantial as possible to enhance our chances of finding effects. The researcher in contact with participants was not aware of the specific instructions given, but contact details of an additional researcher were also given should questions arise during the course of the study. Participants were asked to undertake the intervention for 6 d (days 1–6) with outcomes assessed on day 0 and day 7.

Outcomes

Our primary outcomes were pleasantness and desire to eat for sweet and non-sweet foods and sweet food intake assessed at an ad libitum cold, buffet-style, breakfast meal.

Secondary outcomes were perceived sweet taste intensity of the sweet and non-sweet foods, self-reported adherence to the allocated diet and measures of appetite.

Pleasantness and desire to eat

Pleasantness and desire to eat sweet and non-sweet foods were assessed on each test day using a taste perception test. Participants were instructed to taste and consume bite-sized portions of six different foods (see Table 1), comprised of both sweet and non-sweet items of a range of textures. For the one bite of each food, participants were asked to rate pleasantness and desire to eat on 100 mm visual analogue scales using paper and pen. The instructions for these scales were 'How PLEASANT does this food taste to you right now?' (response anchors: 'not at all pleasant', 'extremely pleasant') and 'Now, rate how strong your DESIRE TO EAT more of this food is right now?' (response anchors: 'not at all strong', 'extremely strong') (19) . The foods were tasted in a prespecified order, and participants were required to take a sip of water between each food item to limit the mixing of flavours. The bite-sized portions were consumed in full to avoid differential impacts on subsequent test meal intake measures. Food order varied between participants in a counterbalanced manner, but it remained the same on day 0 and day 7 for each individual.

Sweet food intake

Sweet food intake was assessed using an ad libitum cold buffet-style breakfast(20) . Participants were presented with a variety of sweet and non-sweet foods and invited to consume as much or as little as they desired. All foods are commonly consumed in the UK and have been used in a previous study to illustrate changes in intake over time(13) . For each participant, foods were individually weighed before and after breakfast to allow calculations of the percentage weight consumed from sweet foods and sweet foods and beverages, percentage of energy consumed from sweet foods and sweet foods and beverages, the weight of sugar consumed from foods and from foods and beverages and percentage of energy consumed from sugar from foods and from foods and beverages. Due to the lack of agreement regarding the most appropriate metric for assessing dietary sweet food intake(21) , several measures of intake were employed.

Sweet taste intensity

Sweet taste intensity was assessed on each test day in the taste perception test as above. For each of the six foods provided participants were also asked to rate sweet taste intensity on paper and pen 100 mm visual analogue scales, using the instruction 'How SWEET does this food taste to you right now?' (response anchors: 'not at all sweet', 'extremely sweet').

Adherence

Adherence to the intervention instructions was assessed at the end of the intervention period. Participants were asked how well they adhered to their allocated diet ('How well did you adhere (manage to keep) to your allocated diet?', response anchors: 'not at all', 'extremely'), how difficult they found it to adhere to their allocated diet ('How difficult did you find it to adhere (manage to keep) to your allocated diet?', response anchors: 'not at all', 'extremely') and how different their allocated diet was from their usual diet ('How different was your allocated diet from your usual diet?', response anchors: 'not at all', 'extremely'). Responses were made using paper and pen 100 mm visual analogue scales and were verified using records of sweet food consumption over the previous day and verbal reports of difficulties over the intervention week.

Appetite

Ratings of hunger, fullness and thirst were also undertaken using paper and pen 100 mm visual analogue scales at the start of each test session to allow for differences in appetite on each test day. Participant age and sex were also collected for descriptive purposes.

Procedure

The study was run from both the University of Bristol, UK (February 2018–May 2018), and from Bournemouth University (January 2023–May 2023, October 2023–March 2024). The initial study began at the University of Bristol and, following disruptions due to COVID-19, was continued later at Bournemouth University. Data collection was carried out at the Nutrition and Behaviour Unit at the University of Bristol and the Eating Behaviours Laboratory at Bournemouth University. Participants visited the testing site fasted and rested on day 0 and day 7 during pre-booked time slots. Visits were scheduled between 08.00 and 11.00, and the timeslots remained the same on both occasions. Upon arrival, participants were seated individually at a table where they were presented with the taste perception test. After completing this test, participants received their cold buffet-style breakfast. The entire procedure lasted approximately 30 min and was repeated exactly on both testing occasions, with three exceptions. At the end of day 0 following all data collection, participants were provided with their dietary intervention. On day 7, participants also completed the adherence questions before the taste perception test, and they were asked about any difficulties experienced over the intervention period. After their breakfast, they were also debriefed about the purpose of the research and thanked for participating in the study. To maintain a researcher-blinded study design, an independent researcher with no contact with participants randomised participants to one of the trial arms using a random number generator. Participants were randomised at a ratio of 1 (increase): 1 (decrease) at the University of Bristol and subsequently at a ratio of 1 (increase): 1 (decrease): 1 (no change) at Bournemouth University, to result in a final sample with a ratio of 2 (increase): 2 (decrease): 1 (no change). Group allocation was concealed using white sealed, opaque envelopes, and throughout the trial, the researcher in direct contact with participants remained unaware of each participant's group allocation. To support the blinding,

participants were asked not to disclose any information about the instructions they received to the researcher conducting the testing. Although it was impossible to blind the participants to their group allocation, they were unaware of the true aim of the trial and the instructions received by other participants. Prior to commencement, the study was registered on Clinicaltrials.gov (Initial Study ID: NCT03427658, registration on 9 February 2018, Complete Study ID: NCT05672017, registration on 5 January 2023). We adhered to our trial registrations in all aspects with the exception that sweet food intake was measured only at breakfast rather than at breakfast and lunch as proposed in the registration for the initial study. The study was run using identical interventions and measures in both locations, with the exception that in Bristol, participants discussed their dietary change with a (independent) researcher and were given the written instruction guide, while in Bournemouth, participants were only provided with the written instruction guide, which included a contact to ask questions

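### No primary outcome, intake metric or taste interaction is named as deciding, and no multiplicity or decision rule is stated for the p = 0.05 threshold

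*Protocol*

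**What the plan says.** - **Primary outcomes.** The Protocol (Outcomes) says: "Our primary outcomes were pleasantness and desire to eat for sweet and non-sweet foods and sweet food intake". It gives no order. The SAP (Data) lists the outcomes without marking any as primary.
- **Intake.** The Protocol (Sweet food intake) points to a "lack of agreement regarding the most appropriate metric for assessing dietary sweet food intake" and says that for this reason "several measures of intake were employed". Protocol and SAP describe four quantities: percentage of weight, percentage of energy, weight of sugar, and percentage of energy from sugar. Each is computed with and without beverages. Neither document names a lead.
- **Models.** The SAP (Analyses) averages each taste rating into a sweet and a non-sweet score and fits condition x time x food type. Intake gets condition x time. No deciding term is named for either.
- **Threshold.** The SAP (Analyses) sets significance at p = 0.05. The only corrections it mentions deal with violated parametric assumptions.
- **Sample size.** The Protocol (Participants) bases forty per intervention group on pleasantness alone, at two-sided 0.05 and power 0.8.
- **Timing.** The last testing window in the Protocol (Procedure) is "October 2023–March 2024". The SAP is dated 26.04.24. The Protocol is headed "Document date: 31.05.25" and is written in the past tense. Neither document dates the unblinding.

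**The concern.** A threshold of 0.05 gives a 5% error rate for one effect named in advance. Here several tests could each be offered as the primary result, and nothing says how they combine. Suppose the weight of sugar changes significantly and the percentage of energy from sweet foods does not. The plan does not tell a reader whether that is a primary effect of sweet exposure or one of eight chances.

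The same gap exists inside each taste ANOVA. Condition x time asks whether liking shifts over all foods. Condition x time x food type asks whether liking of sweet foods shifts relative to non-sweet foods. These are different questions. Even pleasantness, the outcome behind the sample size, therefore has two candidate answers.

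At stake is the meaning of a primary claim. The data and the planned ANOVAs remain usable.

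**Working it through.** **1. The plan's own figure.** For a two-sample comparison, n per group = 2(1.960 + 0.842)² SD²/δ² = 15.70 SD²/δ². The Protocol gives δ = 6–9 mm and SD = 13–17 mm.
- 9 mm, SD 14 mm: 15.70 x 196/81 = 38 (39 with the t distribution), close to forty.
- The ends of the ranges give 33 (9 mm, SD 13 mm) and 127 (6 mm, SD 17 mm).
- A paired t calculation at 6 mm, SD 13 mm gives 39.

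Forty is reachable, though not by one route only. The stated calculation concerns pleasantness at 0.05. No power is given for desire to eat or intake.

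**2. Count of primary tests.** Intake: 4 quantities x 2 = 8. With one interaction per taste rating: 2 + 8 = 10. With both interactions per taste rating: 4 + 8 = 12.

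**3. If the tests were independent.** The chance of at least one false positive is 1 − 0.95^k: 14.3% for k = 3, 33.7% for 8, 40.1% for 10 and 46.0% for 12.

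**4. Allowing for overlap.** The metrics share the same meal, so independence overstates the rate. Null trials were simulated with 40/40/20 participants. This size is an assumption, from forty per intervention group and the 2:2:1 final ratio in the Protocol (Procedure). Each test was an F test between arms on change scores, which is equivalent to condition x time. There were 40,000 runs per setting. Assumed correlations: pleasantness with desire 0.7, taste with intake 0.2, and intake metrics with each other as shown.

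| Correlation among intake metrics | 0.5 | 0.7 | 0.9 | 0.95 |
|---|---|---|---|---|
| Any of ten tests | 31.7% | 26.1% | 19.4% | 17.3% |
| Any of eight intake metrics | 25.9% | 19.9% | 12.5% | 9.9% |
| Holm over ten | 4.3% | 3.5% | 2.5% | 2.2% |

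Outside this model, any of ten gives 36.1% at intake correlation 0.3 and 10.2% if all ten tests correlate at 0.95.

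**5. Pleasantness alone.** If either interaction may be read as the answer: 1 − 0.95² = 9.75% if independent. Simulation gives 9.2–10.1% for sweet/non-sweet correlations of 0–0.6 and SD ratios of 1–1.5.

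**6. Would requiring all three outcomes to succeed solve it?** Only with one named intake metric and one named interaction per taste ANOVA. Suppose pleasantness and desire truly change, with effects large enough to be found nearly always, and intake does not. With eight unranked metrics the rule then passes falsely whenever any intake metric is significant. That is the second row of the table, about 10–26%. With one fixed metric it is about 5%.

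**7. What a rule would achieve.** With one lead intake metric and one interaction per rating, in the same model: any of three without adjustment about 13%; Holm over three 4.4–4.5%; fixed sequence 4.9–5.0%.

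**8. Power cost at Holm's first step**, for a test with 80% power at 0.05 (1.960 + 0.842 = 2.802):
- three tests, 0.05/3 = 0.0167: Φ(2.802 − 2.394) = 66%
- ten tests, 0.05/10 = 0.005: Φ(2.802 − 2.807) = 50%
- twelve tests, 0.05/12 = 0.0042: Φ(2.802 − 2.865) = 47%

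**The case against.** The case for the plan is substantial. All eight metrics are listed in both documents, so dropping one silently would show. The Protocol gives a scientific reason for using several. Pleasantness drove the sample size, which hints at a lead outcome. Because food type was added as a factor, the three-way term is the natural sweet-specific reading of the taste ANOVAs, and condition x time is the natural reading for intake. Whether three distinct constructs need joint error control is debated.

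Most of this stands, but it does not supply a rule. The reason for measuring several metrics does not say what a split result means. The hint from the sample size and the natural reading of the interactions are not written down.

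A reader might infer more than the documents support:
- *That the trial's error rate is 32% or 46%.* Neither document says that any one significant result will be claimed, and neither gives correlations.
- *That the sponsor decided against adjustment.* The SAP is silent, and that is all that can be shown.
- *That metrics were chosen after seeing results, because the SAP postdates testing.* The SAP has one blinded researcher process the data until they are checked. The date of unblinding is not given.
- *That no ranking exists anywhere.* The Protocol says "We adhered to our trial registrations in all aspects", with one exception about the meals measured. The registrations are outside these documents, so the point is limited to the Protocol and SAP.

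**Conclusion.** The point holds as a gap in the decision rule. Three primary outcomes are unordered, eight intake metrics have no lead, the deciding taste interaction is unnamed, and no multiplicity adjustment is stated. The excess over 5% is conditional on reading any one significant primary result as an effect. Its size depends on the assumed correlations and on 40/40/20 participants. Even at an intake correlation of 0.95, the intake metrics alone come to about twice 5%. It limits how primary results may be worded and is worth acting on. It does not undermine the data or the planned models.

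**What to change.** **Only if the analysts are still blinded**, amend the SAP:
1. Name condition x time as the deciding effect for intake, and one interaction for each taste ANOVA.
2. Name one lead intake metric with a reason. Report the other seven as supportive, with estimates and confidence intervals.
3. Use Holm over the three primary tests, or a fixed sequence at 0.05 (for example pleasantness, desire to eat, lead intake metric).

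The cost is wording. Holm carries the three-test power loss shown above. The fixed sequence keeps 0.05 for pleasantness, but later outcomes are confirmatory only if earlier ones succeed.

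**If unblinding has happened**, which the dates make likely, do not choose a lead metric or interaction now. Keep the planned analyses. Beside the unadjusted p-values, show Holm-adjusted ones for all primary tests: ten, or twelve if both taste interactions are interpreted. Label the adjustment post hoc. Do not present an isolated unadjusted significant intake metric as a primary effect. This costs one extra column and no new data. Holm over ten is conservative for metrics that overlap this much (2–4% in the model), and its first step leaves about 50% power, or 47% over twelve. The adjusted values therefore belong beside the planned ones, not in place of them.

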For sweet food intake measures, the weight of foods consumed in grams, will be calculated by subtracting the weight of foods returned to the kitchen from the amount served at breakfast, and used to calculate the percentage weight consumed from sweet foods and the percentage weight consumed from sweet foods and beverages. Manufacturer's information will then be used to calculate the percentage of energy consumed from sweet foods, percentage energy consumed from sweet foods and beverages, the weight of sugar consumed from foods, the weight of sugar consumed from sweet foods and beverages, the percentage of energy consumed from sugar from foods, and the percentage energy consumed from sugar from foods and beverages. Intake will then be analysed using 3 condition (increase sweet food consumption, decrease sweet food consumption, no diet change) x 2 time (day 0, day 7) repeated-measures ANOVAs.

Appetite will be assessed using 3 condition (increase sweet food consumption, decrease sweet food consumption, no diet change) x 2 time (day 0, day 7) repeated-measures ANOVAs, for each of the three measures.

Compliance will be assessed using 3 condition (increase sweet food consumption, decrease sweet food consumption, no diet change) x 2 time (day 0, day 7) repeated-measures ANOVAs.

Correlations between measures in the taste perception test and the subsequent intake measure will also be conducted.

Analyses will be undertaken on an intention-to-treat basis, with missing data imputed using models based on gender, age and baseline data. Per-protocol analyses may also be undertaken dependent on participant drop out and self-reported compliance.

Analyses will be conducted in SPSS (version 28.0.0.0) or Stata (version 15), as required. Data will be presented as means and standard deviations. Significance will be set at $p = 0.05$.

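### The trial took previous-day records of sweet foods but the SAP does not analyse them; comparing them by arm would be a cheap manipulation check

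*Protocol*

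**What the plan says.** The protocol (Intervention/control) sets the exposure period: "Participants were asked to undertake the intervention for 6 d (days 1–6"). Under Adherence it describes three visual analogue scales, completed once at the end: how well the participant kept to the allocated diet, how hard that was, and how far the diet departed from the usual one. It adds that the answers were "verified using records of sweet food consumption over the previous day", together with what participants said about difficulties during the week. It does not give the format of the records, how they were scored, or what happened when a record and a rating disagreed.

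The SAP lists compliance among the outcomes as ratings only. Its Compliance section repeats the three scales, and its Analyses section says: "Compliance will be assessed using 3 condition (increase sweet food consumption, decrease sweet food consumption, no diet change"), crossed with time at day 0 and day 7. A per-protocol analysis is optional and depends on drop-out and self-reported compliance. The records appear nowhere in the SAP.

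**The concern.** The trial asks what a change in sweet exposure does to preference and intake, but the exposure was not controlled. Participants were told to eat more or fewer sweet foods, with no target amount, and were left to judge which foods suited. Delivery also differed by site: Bristol participants discussed the change with a researcher and received the written guide, while Bournemouth participants received the guide alone. How far the arms separated is therefore something to be observed.

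The planned compliance analysis does not observe it directly. If outcomes turn out similar across arms, a reader will ask whether sweet exposure has little effect or whether exposure differed little. The one item described that bears directly on sweet intake during the intervention is the previous-day record, and no analysis of it is planned.

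**Working it through.** **What each source can show about separation between the increase and decrease arms**

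| Source | Rated or measured against | Evidence on separation |
|---|---|---|
| How well adhered | The participant's own instruction | A control who changes nothing can properly score 100; equal means fit large or small separation |
| How difficult | The participant's own instruction | Effort, not sweet intake |
| How different from usual | The participant's own usual diet, no direction | Increase v. decrease: similar means are expected if both arms moved equally far apart and also if neither moved. Against control: indirect evidence that something changed |
| Weighed test breakfast | Days 0 and 7 | A primary outcome, not exposure on days 1–6 |
| Previous-day record | Sweet foods eaten on one day | Direct, though limited; not in the SAP |

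**The plan's own figure.** The protocol's calculation gave "the need for forty participants per intervention group", at two-sided α 0.05 and power 0.80, from changes of about 6–9 mm and SDs of about 13–17 mm. For two independent means, n per arm = 2(1.960 + 0.842)² (SD/δ)² = 15.70 (SD/δ)².
- δ 9, SD 14: 15.70 × 2.420 = 38.0, so 38.
- δ 9, SD 13: 32.8, so 33.
- δ 6, SD 17: 126.02, rounded up to 127.
- A paired t calculation at δ 6, SD 13 gives 39.

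The stated 40 is thus within 2 of the result at some points in the quoted ranges. It is used below only as an arm size, and no sample-size error follows from this point.

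**What a comparison of the records could detect.** The documents give no mean or SD for the records, so the results are in SD units. Arm sizes are 40 in each intervention arm and, from the 2:2:1 ratio under Procedure, 20 controls. Every participant is assumed to have a usable record.

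Detectable difference at 80% power = (1.960 + 0.842) × √(1/n₁ + 1/n₂):
- Increase v. decrease, 40 v. 40: 2.802 × 0.2236 = 0.63 SD.
- Either arm v. control, 40 v. 20: 2.802 × 0.2739 = 0.77 SD.

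Power for a true 1 SD separation = Φ(1/√(1/n₁ + 1/n₂) − 1.960):
- 40 v. 40: Φ(4.472 − 1.960) = Φ(2.512) = 99%.
- 40 v. 20: Φ(3.651 − 1.960) = Φ(1.691) = 95.5%.

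For a true 0.5 SD separation, power is 61% and 45%. The 95% CI half-width for increase v. decrease is 1.960 × 0.2236 = 0.44 SD. The check would therefore show a large separation clearly and leave a moderate one uncertain.

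Increase v. decrease is the cleaner contrast, because those arms were randomised together at both sites. The control arm was randomised only at Bournemouth, and the 40 v. 20 figures ignore site.

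**Dates.** Data collection ran to March 2024 and the SAP is dated 26.04.24. A check added now is therefore specified after data collection.

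**The case against.** Several counter-arguments have force.

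- **The randomised comparison stands without a manipulation check.** A reader might infer that a null result could not be interpreted at all. The documents do not support that. Arms are randomised to an instruction and analysed by intention to treat, so a null still estimates the effect of being given that instruction. Only the further step, to sweet exposure itself, is weakened.
- **The SAP is not silent on separation.** The how-different scale is compared by arm, and a participant who changed little should score low on it. Read with the how-well scale, which refers to a directional instruction, it gives indirect evidence. This stands, but the evidence is self-rated and does not measure sweet intake.
- **The records already have a role as verification.** That is so, but no rule says how they verify a rating or whether they affect the per-protocol set.
- **The records are weak evidence.** They cover one of six days, no baseline record is described, and they appear to come from participants who had been asked to make the change as large as possible. They may share the ratings' demand bias. Their format and completeness are not documented, and their day 7 timing is inferred from the Adherence section, since Procedure does not list them. All of this stands. They offer a snapshot comparison of randomised arms, not proof of six-day exposure or of change from usual diet.
- **Researcher coding may cut across the design**, which deliberately left participants to judge what tasted sweet. This limits how the scoring rule should be written; it does not rule out scoring.

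**Conclusion.** The point holds as a low-cost improvement. A relevant record is described as collected, the SAP does not use it, and the three planned scales give at most indirect evidence that the increase and decrease arms separated. Adding the comparison would help in judging whether a null reflects sweet exposure itself, and the primary analysis would not change.

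Its size cannot be stated from the documents. A reader might be tempted to scale down the expected millimetre effect for partial separation. The documents give neither the separation achieved nor a relation between exposure and effect, so any such figure would be invented. What can be stated is the check's sensitivity: about 0.63 SD for increase v. decrease. This assumes 40 usable records per arm, a normal approximation, and records that were kept in a form that can be scored.

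A related inconsistency needs reconciling in the same section: the compliance ANOVA has a day 0 level, although both documents place the adherence ratings at the end of the intervention only.

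**What to change.** Add a short supplementary section to the SAP, labelled as specified after data collection:

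1. State what the previous-day records contain, when they were taken, and how many are usable in each arm.
2. Score them by one simple rule as far as their format allows, for example the number of sweet items or eating occasions. Where possible, follow the participant's own view of what was sweet. Do not give the coder arm labels.
3. Compare arms, with the increase v. decrease difference and its 95% CI as the main result, reported beside the three adherence ratings.
4. State how the records verify a rating, and how (or whether) they inform any per-protocol set.
5. Replace the two-level time factor in the compliance analysis with a comparison of arms on the end-of-study ratings, or identify the day 0 measurement it refers to.
6. State the limits: apparently self-reported data, one of six days, no described baseline, possible demand bias, and content that may reveal the arm to the coder.

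The cost is the coding of existing records, if they were retained in usable form, and one extra analysis. No new data collection is needed. If the records cannot be scored, the report should say so and describe the evidence for separation as indirect.
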